8.1.2.13. Gastrointestinal Health Questionnaire (GIHQ) Scores

The Gastrointestinal Health Questionnaire (GIHQ) will be completed at all Screening and Baseline visits (Visits 1, 2, 3), as well as Week 6 (Visit 9), End of Treatment (Week 13, Visit 16), and Follow-up (Visit 17). Each item is scored on its frequency, relevancy, and importance to the caregiver. The Frequency is measured on a 5-point scale where 0=never; 1=almost never; 2=sometimes; 3=often; 4=almost always. The surgery domain, however, records frequency as 0=No and 1=Yes. The relevancy is scored on a scale from 1 to 4, where 1 is not relevant and 4 is very relevant. The importance is scored on a scale from 1 to 4, where 1 is not important and 4 is very important. Lower scores indicate fewer gastrointestinal problems. The total score is the sum of all items. The items are grouped into 9 domains. The domain score is the sum of all items within the domain, as shown on the CRF. Missing items will be imputed as defined in section 4.2.3. The domain scores will only be calculated if all items within the domain are answered or can be imputed. The domains are as follows:

- 1. General Health/Pain: Items 1-5, frequency score ranges from 0-20, relevancy score ranges from 5-20, importance score ranges from 5-20.
- 2. Eating, Chewing, and Swallowing: Items 1-9, frequency score ranges from 0-36, relevancy score ranges from 9-36, importance score ranges from 9-36.
- 3. Reflux: Items 1-3, frequency score ranges from 0-12, relevancy score ranges from 3-12, importance score ranges from 3-12.
- 4. Gas and Bloating: Items 1-5, frequency score ranges from 0-20, relevancy score ranges from 5-20, importance score ranges from 5-20.

- 5. Diarrhea and Constipation: Items 1-6, frequency score ranges from 0-24, relevancy score ranges from 6-24, importance score ranges from 6-24.
- 6. Personality and Mood: Items 1-5, frequency score ranges from 0-20, Relevancy score ranges from 5-20, importance score ranges from 5-20.
- 7. Medications: Items 1-9, frequency score ranges from 9-36, relevancy score ranges from 9-36, importance score ranges from 9-36.
- 8. Surgery: Items 1-5, frequency score ranges from 0-5, relevancy score ranges from 5-20, importance score ranges from 5-20.
- 9. Parenting: Items 1 8, frequency score ranges from 0 24, relevancy score ranges from 8 24, importance score ranges from 8 24.

Within subject change is the difference between the score at each timepoint and the score at Baseline (Visit 3). Summary statistics for the change from baseline in the total and each GIHQ domain score will be displayed at all post-baseline visits. Test-retest reliability will be assessed for all scores collected during the Screening period (Visits 1, 2, and 3, pre-dosing) using Intraclass Correlation Coefficients (ICC). Changes from baseline will be analyzed using a Wilcoxon signed rank test. The total score will be presented in waterfall plots, histograms, and violin plots, and the domain scores will be presented in a forest plot, as described in Section 8.1.2.

8.1.2.14. Vineland Adaptive Behavior Scales-3 (VABS-3)

The Vineland Adaptive Behavior Scales-3 will be completed at Baseline (Visit 3) and End of Treatment (Week 13, Visit 16). Scores are calculated by the site rater. An Adaptive Behavior Composite (ABC) standard score will be recorded, along with a standard score for each of the 4 domains: Communication, Daily Living Skills, Socialization, Motor Skills. For the motor skills domain, scores can only be calculated for participants ages 3-9. These range from 20 to 140.

In each of the 11 subdomains, the raw scale (range 0 to 116), v-scale (range 1 to 24), age equivalent (range 0:0 to 22:0+), and growth scale (range 10 to 197) scores are recorded. Lower scores reflect less adaptability. If a score is missing, that subject will be excluded from corresponding summaries. Within subject change is the difference between the score at EOT and the score at Baseline (Visit 3).

Summary statistics for the change from baseline in the Vineland Adaptive Behavior Scales-3 composite and domain standard scores, and subdomain raw, v-scale, and growth scale scores will be displayed at end of treatment. Changes from baseline will be analyzed using a Wilcoxon signed rank test. The composite standard score will be presented in waterfall plots, histograms, and violin plots, and the domain standard scores will be presented in a forest plot, as described in Section 8.1.2.

8.1.2.15. Quality of Life Inventory—Disability (QL-Disability)

The Quality of Life Inventory—Disability (QL-Disability) Score will be completed at Baseline (Visit 3) and at the End of Treatment (Week 13, Visit 16). Each item is scored on a 5-point scale, where 1=never; 2=rarely; 3=sometimes; 4=often; 5=very often. The items are grouped into five domains: health and well-being (items 1-4), feelings and emotions (items 5-15), family and friends (items 16-22), activities and the outdoors (items 23-27) and Daily Life (items 28-32). The domain scores are calculated by first transforming the 5-point scale, so that 1=0, 2=25, 3=50, 4=75, and 5=100. Items 9-15 are reversed in scoring, so that 1=100, 2=75, 3=50, 4=25, and 5=0. The domain score is the average of the transformed score of the items within that domain. Missing items will be imputed as defined in section 4.2.3. A domain score will be calculated as long as at least one of the items within the domain is answered. The overall score is the average of all domain scores and will be calculated as long as at least one of the domain scores can be calculated. Higher scores indicate a better quality of life. Within subject change is the difference between the score at EOT and the score at Baseline (Visit 3).

Summary statistics for the observed and change from baseline in the QL-Disability overall and domain scores will be displayed at end of treatment. Changes from baseline will be analyzed using a Wilcoxon signed rank test. The overall score will be presented in waterfall plots, histograms, and violin plots, and the domain scores will be presented in a forest plot, as described in Section 8.1.2.

8.1.2.16. Impact of Childhood Neurological Disability (ICND) - Overall quality of life rating

The Impact of Childhood Neurological Disability (ICND) Scale will be administered at Baseline (Visit 3) and at End of Treatment (Week 13, Visit 16). The ICND is scored on a scale from 1 to 6, where 1=poor and 6=excellent. Lower scores indicate greater negative impact on quality of life. Within subject change is the difference between the score at EOT and the score at Baseline (Visit 3). If a score is missing, that subject will be excluded from corresponding summaries.

Summary statistics for the observed and change from baseline in the ICND score will be displayed at end of treatment. Change from baseline will be analyzed using a Wilcoxon signed rank test. The overall score will be presented in waterfall plots, histograms, and violin plots, as described in Section 8.1.2.

8.1.2.17. Stanford-Binet Intelligence Scales (SB5)

The Stanford-Binet Intelligence Scales (SB5) will be performed at Screening and Visit 16 (end of treatment). Participants who cannot be assessed on the SB-5 due to their

developmental level will be assessed using the Mullen Scales of Early Learning instead. General cognitive ability is reported as a full scale intellectual quotient score (FSIQ). Cognitive ability in five categories is reported in the index scores: fluid reasoning (FR), knowledge (KN), quantitative reasoning (QR), visual-spatial processing (VS), and working memory (WM). Non-verbal (NVIQ) and verbal intelligence quotients (VIQ) are also recorded. Scores range from 40 to 160, where higher scores indicate a higher IQ. For the analysis of index scores and IQ, the z-deviation method for intellectual disability will be used (Sansone et al. 2014). Standard scores, change-sensitive scores, age equivalents and the raw scores were calculated and entered by the site rater. Z-deviation scores were derived using the algorithm in R code from the algorithm developer (Translational Psychophysiology and Assessment Laboratory (T-PAL),

MIND Institute, University of California, Davis, Sacramento California). For age equivalent values < 2, the result is entered into EDC as 1.9, for analysis. For age equivalent values > X, where X is a numeric value, the result is entered into EDC as X.1, for analysis. For example, ">33" is entered in EDC as 33.1.

Summary statistics on the observed and change from baseline in the z-deviation scores, change-sensitive scores and age equivalents for FSIQ, NVIQ, VIQ, and the domain scores: FR, KN, QR, VS, WM. Each category will be displayed at end of treatment. The FSIQ, NVIQ, and VIQ z-deviation scores will be presented in waterfall plots, histograms, and violin plots, and the domain z-deviation scores will be presented in forest plots, as described in Section 8.1.2.

8.1.2.18. Mullen Scales of Early Learning

The Mullen Scales of Early Learning (MSEL) will be performed at Screening and Visit 16 (end of treatment) on those subjects who cannot be assessed using the SB5. It assesses developmental and cognitive functioning in five categories: gross motor (GM), visual reception (VR), fine motor (FM), expressive language (EL), and receptive language (RL). All scores except the developmental quotients are calculated by the site rater. A raw score, age equivalent score and developmental quotient will be recorded for each category for all participants. As part of the analysis, an overall developmental quotient, a verbal developmental quotient, and a non-verbal developmental quotient will also be calculated as follows:

Overall Developmental Quotient:

(Mean of the age-equivalent scores in months of the fine motor, receptive language, expressive language, visual reception scales/chronological age in months) x 100

Verbal Developmental Quotient:

(Mean of the age-equivalent scores in months of the expressive and receptive language scales/chronological age in months) x 100

Non-verbal Developmental Quotient:

(Mean of the age-equivalent scores in months of the visual reception and fine motor scales/chronological age in months) x 100

Chronological age in months will be calculated as (date of assessment – date of birth + 1)/30.4375.

For each of the five domains, a t-score will be recorded for participants \leq 68 months old. An Early Learning Composite score will be recorded a long with its band of error for participants \leq 68 months old.

For age equivalent values < 2, the result is entered into EDC as 1.9, for analysis. For age equivalent values > X, where X is a numeric value, the result is entered into EDC as X.1, for analysis. For example, ">33" is entered in EDC as 33.1.

The domain raw scores have an average of 50 and a standard deviation of 10. The composite standard score has a mean of 100 and a standard deviation of 15. The developmental quotient scores are a ratio of developmental age to chronogical age and will have a range of 1 to 100. Higher scores indicate a higher IQ or better developmental progress. If any scores are missing, the subject will be excluded from corresponding summaries.

Summary statistics on the observed and change from baseline in the composite standard score, developmental quotient scores, age equivalent scores, and each category t-score will be displayed at end of treatment. The composite standard score and overall, verbal, and non-verbal developmental quotient scores will be presented in waterfall plots, histograms, and violin plots. The domain developmental quotient scores will be presented in forest plots, as described in Section 8.1.2.

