- Obsessive-compulsive Disorder will be derived from the PMS diagnosis page on the CRF. If "Obsessive-compulsive disorder" is checked to the under "confirmation of psychiatric co-morbidities", the subject is considered as having the disorder.
- Dose modification is defined as dose increased, dose reduced, or dose interrupted responses for the action taken with study treatment on the adverse event (AE) CRF.
- Improvement in the top 3 concerns will be derived as a decrease in severity (change from baseline <0).
- Baseline seizure frequency will be determined based on the number of seizures recorded in the diary during the 4–6-week screening period. The baseline monthly seizure frequency will be derived by dividing the total number of seizures during the screening/baseline period by the screening/baseline duration in months ([first dose date screening date] divided by 30.4375). The baseline weekly seizure frequency will be derived by dividing the total number of seizures during the screening/baseline period by the screening/baseline duration in weeks ([first dose date screening date] divided by 7). During the treatment period (Visits 4 16), the seizure frequency will be derived by summing the number of seizures recorded in the diary over treatment. The monthly seizure frequency will be derived by dividing the total number of seizures during the treatment period by the treatment duration in months (treatment duration divided by 30.4375). The weekly seizure frequency will be derived by dividing the total number of seizures during the treatment period by the treatment duration in weeks (treatment duration ([first dose date screening date] divided by 7).
- The Mullen Scales of Early Learning developmental quotient (DQ) is calculated as the (mean of the age equivalent in months of the corresponding scales/chronological age in months) x 100. For the overall DQ, the mean of the fine motor, receptive language, expressive language, visual reception is included. For the non-verbal DQ, the mean of the fine motor and visual reception scales are included. For the verbal DQ, the receptive language and expressive language scales are included.
- For the Mullens Scales of Early Learning and the Stanford-Binet 5, Chronological age in months will be calculated as (date of assessment date of birth + 1)/30.4375.

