7.1. Efficacy Variables

There are no primary efficacy variables.

Secondary variables for efficacy to be considered include:

- PMS-specific Clinical Global Impression Scale—Overall Improvement (CGI-I)
 Score
- PMS-specific Clinical Global Impression Scale–Domain Improvement Scores
- PMS Domain Specific Rating Scale Improvement Scores
- Caregiver Impression of Change Score
- Clinical Global Impression Scale-Severity (CGI-S)-Overall Severity Score
- Clinical Global Impression Scale-Severity (CGI-S)-Domain Scores
- MacArthur-Bates Communicative Development Inventory (MB-CDI) Scores
- Observer-Reported Communication Ability (ORCA) Score
- Caregiver Top 3 Concerns Likert Scale Scores
- Aberrant Behavior Checklist-2 (ABC-2) Scores
- Behavior Problems Inventory-Short Form (BPI-SF) Scores
- Child Sleep Habits Questionnaire (CSHQ) Scores
- Gastrointestinal Health Questionnaire (GIHQ) Scores
- Vineland Adaptive Behavior Scales-3 Growth Scale Scores
- Quality of Life Inventory-Disability (QI-Disability) Scores
- Impact of Childhood Neurological Disability (ICND) Overall quality of life rating
- Stanford-Binet raw, z-deviation, age-equivalent, and Change Sensitive scores or Mullen Scales of Early Learning raw, age-equivalent and Developmental Quotient scores

Biomarker variables and gut microbiome analyses will be described in a separate analysis plan.

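### A child at the ceiling of a Mullen scale at both visits is always recorded as declining on that scale's own developmental quotient (DQ), because the capped age equivalent is divided by a rising age

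*SAP*

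**What the plan says.** The Mullen is given at Screening and at Visit 16 to children who cannot be assessed on the Stanford-Binet (SAP 8.1.2.18). The same section sets the entry rule for a value above the scale's range: "For age equivalent values > X, where X is a numeric value, the result is entered into EDC as X.1, for analysis". Its worked example turns >33 into 33.1. Values below 2 are entered as 1.9.

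SAP 4.3 states that the DQ "is calculated as the (mean of the age equivalent in months of the corresponding scales/chronological age in months) x 100". Both 4.3 and 8.1.2.18 take chronological age from the date of each assessment, so it rises between the two visits. For the individual scales, 8.1.2.18 says: "A raw score, age equivalent score and developmental quotient will be recorded for each category for all participants". Overall, verbal and non-verbal DQs average four, two and two scales respectively, and gross motor enters none of them.

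Observed values and change from baseline are summarised for the composite standard score, the DQs, the age equivalents and the t-scores. For single scales, "The domain developmental quotient scores will be presented in forest plots". Higher scores are to be read as better. SAP 7.1 names as efficacy variables the "Mullen Scales of Early Learning raw, age-equivalent and Developmental Quotient scores", but the list of change summaries in 8.1.2.18 leaves out the raw scores. Neither document has a rule for a child at the ceiling at both visits.

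**The concern.** An age equivalent reported as >X is right-censored: the child is somewhere above X and the scale cannot say where. Entering X.1 at both visits makes the recorded gain exactly zero. Dividing that constant by a larger age then turns no recordable change into a recorded loss. In the DQ change table and the forest plot this child looks the same as one who really fell behind. It would pull down the mean DQ change on that scale in a study with about 20 planned completers, only some of whom take the Mullen.

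The situation is foreseeable. The SAP provides a ceiling rule, and children from 3 to 12 years are enrolled on a test that Protocol 9.5.9.4 describes as designed for 0 to 68 months.

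**Working it through.** **Inputs**
- Entry rule and example: SAP 8.1.2.18. With X = 33, 33 + 0.1 = 33.1, which reproduces the SAP's figure.
- DQ = 100 × AE / CA, with AE the age equivalent and CA the chronological age, both in months (SAP 4.3, 8.1.2.18). Months are days / 30.4375.
- Interval between tests: a Screening/Baseline period of 4 to 6 weeks (Protocol 9.1) plus 13 weeks of treatment (Protocol 9.4.2). That is 17 to 19 weeks, or 119 to 133 days: 119 / 30.4375 = 3.91 and 133 / 30.4375 = 4.37 months.
- Ages: 3 to 12 years (Protocol 8.1).

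**Direction.** With AE the same at both visits, DQ2 / DQ1 = CA1 / CA2. This is below 1 whenever time has passed, whatever the value of X.

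**Size for one scale, 33.1 at both visits.** Changes are computed before rounding.

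| Age at Screening (months) | DQ at Screening | DQ at EOT, 119 days (change) | DQ at EOT, 133 days (change) |
|---|---|---|---|
| 36 | 91.94 | 82.94 (-9.01) | 81.99 (-9.95) |
| 48 | 68.96 | 63.76 (-5.19) | 63.20 (-5.75) |
| 72 | 45.97 | 43.60 (-2.37) | 43.34 (-2.63) |
| 144 | 22.99 | 22.38 (-0.61) | 22.31 (-0.68) |

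Example: at 36 months over 119 days, 100 × 33.1 / 36 = 91.94 and 100 × 33.1 / 39.91 = 82.94. The relative fall over 119 days runs from 9.8% at 36 months to 2.6% at 144 months and does not depend on X. If the ceiling were 68 (an assumption; the documents give only a design range), the 119-day fall would be 4.87 points at 72 months and 1.25 at 144.

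**How much of the fall is artefact.** If the true but unrecorded gain is g months, the shortfall is 100 × g / CA2. A child who kept pace with age would have gained 33.1 × 3.91 / CA1: 3.59 months at age 36, 2.70 at 48, 1.80 at 72 and 0.90 at 144. Putting these into the formula returns the whole tabulated fall, for example 100 × 3.59 / 39.91 = 9.0. With a true gain of 1 month at age 48, the artefact is 100 × 1 / 51.91 = 1.93 of the 5.19 points. With no true gain it is zero.

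**Combined DQs.** Take a child of 48 months over 119 days whose other scales start at 24 months and keep pace with age (assumed). The overall DQ changes by -1.30 with one of four scales at the ceiling, -2.60 with two and -5.19 with all four. With one scale at the ceiling, a gain of 2.85 months on each of the other three would hold the overall DQ level.

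**Longer interval.** Protocol 9.5.9.4 lets a Mullen from up to 3 months before Screening stand in for the Screening test. If age is taken at that earlier date, the interval can reach about 133 + 91 = 224 days (7.36 months), and the fall for a child aged 36 months at the first test is 15.61 points.

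**The case against.** The best reply is that this is narrow and of little consequence, and much of that stands.

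- Any unchanged age equivalent lowers a ratio DQ, at the ceiling or not. So the tabulated falls are not artefact in full unless the child kept pace with age.
- A reader might infer that every planned Mullen change summary is distorted. The documents do not support that. Recorded age-equivalent change is 0, not negative. Composite and t-scores come from the site rater and do not use the ratio, though they exist only for children up to 68 months.
- A reader might also infer that the combined DQs must fall. They need not, since gains on other scales can offset a capped one.
- The Mullen goes only to children who cannot be assessed on the Stanford-Binet, in a disorder with mostly moderate to profound intellectual disability, so ceilings may be rare. The >33 example also appears word for word in the Stanford-Binet section, so the documents do not establish 33 as a Mullen ceiling. The 36-month case implies a scale DQ near 92, which is unlikely to be typical.
- There is no primary efficacy endpoint, all significance levels are nominal (SAP 7.5, 8.1.1), and Protocol 6.3.2.1 does not list the Mullen. The error makes a child look worse on treatment, so it cannot create a false signal of benefit.

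None of this removes the defect. For a child at the ceiling of a scale at both visits, a rule the SAP itself states yields a recorded decline that may not be real, and nothing elsewhere in the plan marks it.

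**Conclusion.** The point holds for a scale's own DQ and no further. A child at the ceiling of a Mullen scale at Screening and at end of treatment is always recorded as declining on that DQ: by 9.01 to 9.95 points at 36 months, 5.19 to 5.75 at 48 and 0.61 to 0.68 at 144, for 33.1 at both visits over 119 to 133 days. Keeping pace with age is taken as the upper case, in which the whole fall is artefact.

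These figures rest on the SAP's example value and the planned visit interval. No shift in the group mean can be given, because neither the number of children taking the Mullen nor the number at a ceiling is stated. The safety and pharmacokinetic objectives are untouched. This is a cheap improvement to a secondary, descriptive measure, not a threat to the study's conclusions.

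**What to change.** In SAP 8.1.2.18, before database lock:

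1. Flag every age equivalent recorded as >X, and report the number of children per scale and visit.
2. Present each scale's DQ change, and any overall, verbal or non-verbal DQ that contains a flagged scale, with and without children at the ceiling at both visits.
3. Do not exclude floor values (<2 entered as 1.9). The same arithmetic applies there but is small (5.28 to 4.76 at 36 months over 119 days), and dropping children who may have made no progress could tilt the mean toward benefit.
4. Summarise raw-score change from baseline for all five scales, in line with SAP 7.1, with a note that raw scores may also be limited at the ceiling.

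The cost is one flag, a few extra table rows and a smaller n in the summaries without ceiling values. Raw scores are already recorded for every category and participant, so no new data are needed.

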8.1.3. Exploratory Efficacy Analysis

8.1.3.1. Biomarkers and gut microbiome

Blood and stool samples will be collected at Screening (Visit 1), Baseline (Visit 3, before dosing), and at End of Treatment (Visit 8), or upon early termination. Biomarkers and gut microbiome will be analyzed separately outside of this analysis plan.

